Thursday June 3rd, 2021

TITLE: Enhancing Cognition in Older Persons: A Randomized Controlled Trial of Mindfulness-Based Stress Reduction (MBSR) and Transcranial Direct Current Stimulation (tDCS).

NCT03653351

METHODS

Study design and participants

We conducted a randomized, double blind, sham-controlled trial of tDCS combined with MBSR in adults aged 60 years or older with symptoms of depression or anxiety plus subjective cognitive complaints in two academic centers (Centre for Addiction and Mental Health, Toronto, ON, Canada; and Washington University in St. Louis, MO, USA). The study was approved by both institutional review boards and all participants provided written informed consent.

Participants were recruited between June 27, 2018 and March 6, 2019. They completed an initial phone screen followed by an in-person screening assessment, which included a review of medical history and medications to determine eligibility. Participants reported cognitive complaints but had intact cognitive function as ascertained by a Short Blessed Test [27] score ≤ 10 and a Montreal Cognitive Assessment (MoCA; [28]) score ≥ 25 . The Patient Reported Outcomes Measurement Information System (PROMIS) measures were used to assess depression and anxiety over the past seven days [29] including self-reported negative mood, views of self, social cognition, decreased positive affect, engagement self-reported fear, anxious misery, hyperarousal, and somatic symptoms related to arousal [30]. Participants were included if their baseline PROMIS 8-item depression score was ≥ 16 or their baseline PROMIS 7-item anxiety score was ≥ 14 , indicating moderate to severe symptoms.

Exclusion criteria included unstable medical illness, metal implants, significant neurological conditions, use of cognitive enhancers (e.g., donepezil) within the past 6 weeks, use of anticonvulsants or antipsychotics (other than low-dose aripiprazole (\leq 2mg) or low dose gabapentin (\leq 100mg) if prescribed for pain), current cognitive training with brain training software, regular participation in mindfulness practice or yoga, IQ $<$ 70 as estimated by the Wechsler Test of Adult Reading (WTAR; [31]), lifetime diagnosis of bipolar disorder, schizophrenia, schizoaffective disorder, or untreated post-traumatic stress disorder, or substance abuse within six months, as diagnosed by the Mini-International Neuropsychiatric Interview (MINI; [32]). Participants meeting all eligibility criteria completed the baseline assessments, which included self-report and neuropsychological assessments of outcomes, listed below.

Interventions

All participants received MBSR; they were randomly assigned (1:1) to active or sham tDCS, using a permuted block approach to ensure treatment balance within each study site. Participants, MBSR instructors, and outcome raters were blinded to the tDCS condition (i.e., active vs. sham). Following the protocol of a large trial assessing the efficacy of combining tDCS with cognitive remediation in preventing dementia among older adults with mild cognitive impairment or remitted depression [33], active tDCS administration involved applying excitatory bilateral stimulation to the left and right DLPFC. To achieve this bilateral stimulation, the anode was placed at Fz and the cathode at Iz as per the 10-20 international electrode placement system. The tDCS was applied using a direct current of 2 mA (current density of 0.57 A/m^2) for 30 minutes per day [33].

during meditative practices of MBSR. The same parameters were used for sham stimulation, except the device shut off after 30 seconds of active stimulation. This brief period of active stimulation is not known to produce active neurological effects, but does ensure blinding because it is associated with common side effects of active tDCS, such as tingling and itching under the electrodes [34-36].

Prior to the initiation of the intervention, all participants completed tDCS training provided at the local academic hospital using a group format. During five one-hour group sessions provided over five consecutive days, participants were given an overview of the tDCS device and detailed instructions for administration, programming, resetting, electrode placement, and safety procedures (such as aborting sessions safely). They were also trained on how to troubleshoot tDCS problems, such as managing side effects e.g. tingling and itching, and self-record necessary data. At the end of training, participants were required to demonstrate their competency self-administering tDCS by passing an assessment administered by the study coordinators. Throughout the tDCS training sessions and the intervention trial, participants had access to a training video detailing the procedures to guide them through tDCS administration as needed. A manual and coordinator contact information was also provided to each participant, and the study coordinator was available to troubleshoot over the phone during at-home tDCS sessions.

The MBSR training was based on the program developed by Jon Kabat-Zinn at the Center for Mindfulness University of Massachusetts Medical School [14, 15]. The in-class MBSR training was conducted at the academic hospital using a group format over

approximately ten weeks; group sessions included an orientation session, 8 weekly 2.5-hour classes, and a half-day retreat. All participants were required to attend the MBSR in-person classes and instructed to refrain from discussing tDCS treatment amongst themselves to protect blinding. Content included instruction in mindfulness meditation, mindful movements, and discussion of home practices to enhance mindfulness in everyday life. At the end of each in-class session, the MBSR instructor gave the group a structured MBSR activity and associated audio files to complete at home for the week. The study used “A Mindfulness-Based Stress Reduction Workbook” as a companion guide [37]. In summary, participants attended weekly in-class group MBSR plus tDCS sessions at the hospital, and then asked to complete at least 30 minutes of guided MBSR and tDCS at home the other six days of the week.

Outcomes

Trained research staff blinded to participants’ tDCS assignment performed pre- and post-intervention assessments. Follow-up assessments were performed within two weeks of completing the intervention. Feasibility was assessed by examining participants’ in-class attendance (i.e., number of in-person MBSR group sessions attended) and adherence to at-home mindfulness practice while using tDCS. Participants completed hand-written logs daily, detailing their at-home use of tDCS and the frequency and duration of MBSR practice; these self-report logs were used to determine the at-home adherence rates. To determine the at-home adherence rate, we first determined how many at-home sessions each participant completed by looking through the at-home logs. We then calculated the

total expected number of sessions that should have been completed at home over the period of the intervention. Lastly, we divided the total number of sessions each participant completed by the total number of expected sessions to get a percentage of at-home adherence. Participants also documented any failures of the tDCS device during stimulation and any adverse events (AEs). AEs that required the discontinuation of tDCS or MBSR were identified, as were serious adverse events (SAEs) defined as AEs that resulted in life-threatening health issues, hospitalization, or death.

The main cognitive measure was the Fluid Cognition Composite from the National Institutes of Health (NIH) Toolbox Cognition Battery [38], a computer-based instrument measuring both crystallized and fluid cognition. In addition, immediate memory and delayed recall were measured using a standard 16-word list validated at the Washington University Alzheimer's Disease Research Center that is sensitive to change and does not have ceiling effects in preliminary studies.

The Cognitive Affective Mindfulness Scale – Revised (CAMS-R; [39]) was used to measure the four domains of mindfulness – attention, present-focus, awareness, and acceptance. CAMS-R is a self-report measure of everyday mindfulness that is not specific to any one type of meditation. CAMS-R asks questions about translating and integrating the domains of mindfulness into everyday life, for example, being able to focus on the present moment, and keeping track of one's thoughts and feelings. CAMS-R

was administered pre- and post-intervention to determine how well participants integrated the teachings from MBSR into their everyday lives.

In addition to the PROMIS measures of depression and anxiety, the two following PROMIS measures were used to assess satisfaction with, and ability to perform usual social roles and activities: the 8-item short form v2.9 PROMIS Scale for Satisfaction with Social Roles and Activities [40] and the 8-item short form v2.0 PROMIS Ability to Participate in Social Roles and Activities [40].

Statistical Analyses

All data were analyzed using the Statistical Program for Social Sciences (SPSS) version 25.0 [41]. Extreme outliers (± 3 standard deviations) were removed for each time point. Data were visually inspected for normal distribution and were checked statistically with the Shapiro-Wilk test. Chi-square and independent samples *t*-tests were used to evaluate differences between the active and sham tDCS groups on baseline demographic, clinical, and cognitive measures.

Measures of feasibility, tolerability, and safety were analyzed descriptively. While the primary goal of this pilot study was to assess feasibility, tolerability, and safety, preliminary evaluations of changes in efficacy measures were performed using repeated measures analyses of variance (RM-ANOVAs), with randomization as the between-subjects variable, and time-point (pre- or post-intervention) as the within-subjects

variable. For cognition, the three dependent variables were: NIH Toolbox Cognition Battery Fluid Cognition Composite, total recall score of the word list, and the delayed recall score of the word list. The effects of the intervention on subjective changes were explored with the following five dependent variables: CAMS-R, PROMIS depression scores, PROMIS anxiety scores, PROMIS satisfaction with social roles and activities, and PROMIS ability to participate in social roles and activities. For this pilot trial, a $p < 0.05$ was considered significant and no corrections were made for multiple comparisons.

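### PROMIS depression and anxiety select participants and are also pre-post outcomes, so regression to the mean can enter their time effect; the plan does not restrict efficacy conclusions to the active-versus-sham contrast

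*Combined protocol and SAP*

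**What the plan says.** Under Study design and participants, the entry rule is a one-sided cut on either of two symptom scores: "Participants were included if their baseline PROMIS 8-item depression score was ≥ 16 or their baseline PROMIS 7-item anxiety score was ≥ 14". The PROMIS measures "were used to assess depression and anxiety over the past seven days", so the reading covers a short window. The same section closes its eligibility text with: "Participants meeting all eligibility criteria completed the baseline assessments, which included self-report and neuropsychological assessments of outcomes, listed below".

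Under Interventions: "All participants received MBSR; they were randomly assigned (1:1) to active or sham tDCS". There is no wait-list or untreated arm.

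Under Outcomes, blinded staff "performed pre- and post-intervention assessments", and "Follow-up assessments were performed within two weeks of completing the intervention". One pre and one post occasion are described.

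Under Statistical Analyses: "The effects of the intervention on subjective changes were explored with the following five dependent variables: CAMS-R, PROMIS depression scores, PROMIS anxiety scores", followed by two social-role scales. The model is an RM-ANOVA with randomised arm between subjects and time (pre, post) within subjects. The significance level is 0.05 per test, without multiplicity correction. The plan does not say whether the time effect or the arm × time interaction is the efficacy test, and it does not mention regression to the mean.

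**The concern.** People are admitted because a fluctuating seven-day symptom score happened to be high enough on one occasion. Part of that height is transient. If the same reading then serves as the starting point for change, the average is expected to fall at the next measurement even if neither MBSR nor tDCS does anything.

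The RM-ANOVA yields both a time effect and an arm × time effect, and the plan does not say which one supports a conclusion. A significant fall over time in depression or anxiety could therefore be reported as benefit of MBSR or of the combined programme, or its size carried into the planning of a later trial, when some or all of it came from the entry rule. Since every participant receives MBSR, nothing in the design can separate the two.

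**Working it through.** The plan gives no sample size, SD, test-retest correlation, screening distribution or expected PROMIS change. There is no stated figure to reproduce, and every size below rests on assumptions.

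**Inputs from the documents.** Entry if depression ≥ 16 or anxiety ≥ 14; one pre and one post occasion; 1:1 allocation; two-factor RM-ANOVA; p < 0.05.

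**Assumed inputs.** Test-retest correlation r = 0.6 to 0.8. Cut-off c = 0.5 to 1 SD above the screened-pool mean on each scale. Correlation 0.6 between the stable parts of depression and anxiety. Same-day errors on the two scales either independent or correlated 0.6. Total n = 20 to 40. No treatment effect. The admitting score is the pre value.

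**Step 1, a single cut-off as orientation.** Expected fall, in screened-pool SDs, = (1 − r) × φ(c) / (1 − Φ(c)). At r = 0.7 and c = 0.5 this is 0.3 × 0.352 / 0.309 = 0.34 SD.

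**Step 2, the either-scale rule.** A participant need be high on only one scale, so the fall per scale is smaller, but it occurs on both. I simulated 2,000,000 screened persons per scenario, kept those with either reading at or above the cut, and took the mean m and SD s of the depression change.

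**Step 3, chance of a significant fall.** With δ = √n × m / s, the probability is P(T > t₀.₉₇₅), where T is noncentral t on n − 1 degrees of freedom. This is the paired test, which is very close to the RM-ANOVA time effect with equal arms. Example: r = 0.7, c = 0.5, errors correlated 0.6 gives m = 0.23 and s = 0.75; at n = 30, δ = 5.48 × 0.23 / 0.75 = 1.68 and the probability is 37%.

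| Same-day errors | Fall in depression (SD), r 0.8 and c 0.5, to r 0.6 and c 1 | Chance of a significant fall, n = 20 to 40 |
|---|---|---|
| Independent | 0.10 to 0.27 | 9% to 45% |
| Correlated 0.6 | 0.16 to 0.44 | 18% to 88% |

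The nominal chance of a significant fall in a two-sided 5% test is 2.5%. Whether same-day errors are shared matters about as much as reliability or the position of the cut. A lower cut shrinks the effect: at c = 0 with r = 0.9 the fall is about 0.05 SD.

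**Step 4, the randomised contrast.** With two occasions, arm × time is a t-test on change between arms. Both arms pass the same entry rule, so the expected fall cancels. Simulated rejection under no effect was 4.7% to 5.6%, even with the admitting score as pre.

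**Step 5, a separate pre reading.** If PROMIS was repeated after eligibility and that reading is the pre value, the expected artefact is zero when all occasions are equally correlated. If correlation decays with time (screen-to-pre 0.8 to 0.9, pre-to-post 0.6 to 0.8, c = 0.5, depression-anxiety correlation 0.7), 0.13 to 0.30 SD remains.

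**The case against.** Three points stand on the other side.

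First, the premise is not certain. The eligibility text places self-report baseline assessments after eligibility has been met, so a second PROMIS administration is possible. A reader might infer that a fall without treatment is guaranteed. The documents do not support that: they call the admitting score baseline and describe no separate screening PROMIS, but they do not exclude a repeat.

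Second, a reader might infer that the plan commits itself to presenting pre-post change as treatment benefit. It does not. Its phrase about effects of the intervention refers to outcomes analysed in a model that includes randomised arm, and no planning effect size is announced. What remains is an omission: arm × time is not named as the efficacy term, so the time effect is left open to that use.

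Third, the primary goal is feasibility, safety and tolerability, the efficacy analyses are called preliminary, and only two of five subjective outcomes are affected. This limits the severity but does not remove the point, because the change analyses are still planned and tested at 0.05.

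A reader might also infer that the tDCS comparison is biased. It is not, as step 4 shows.

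**Conclusion.** The point holds in conditional form. On the plain reading that the admitting PROMIS score is the pre value, regression to the mean contributes to the time effect for PROMIS depression and anxiety in both arms, and the design has no arm that could remove it. Arm × time is unaffected.

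Under the assumed ranges (r 0.6 to 0.8, cut 0.5 to 1 SD above the screened-pool mean, 20 to 40 participants), the untreated fall in depression is about 0.1 to 0.45 SD, and the chance of a significant fall is roughly 9% to 88%. The spread depends heavily on whether same-day depression and anxiety errors are correlated. These figures illustrate the size and are not bounds, because the documents fix none of the inputs. Severity is minor to moderate.

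**What to change.** In Statistical Analyses, name arm × time, or an ANCOVA of the post score adjusted for baseline, as the only efficacy test for PROMIS depression and anxiety. Report their time effects as uncontrolled, and draw no efficacy claim and no planning effect size from them. State which PROMIS reading is the pre value; if one was taken after eligibility, use that one, noting that it may not remove the artefact entirely.

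Recruitment closed on March 6, 2019, so adding a repeat PROMIS before training is no longer possible in this trial. A successor trial could separate the screening reading from the outcome baseline.

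The cost is a few sentences and no new data. The downside is that within-group improvement on these two scales cannot be claimed as benefit.

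### Allocation was blocked within site, but the efficacy RM-ANOVA omits site; if the sites differ in mean pre-post change, the arm-by-time test is conservative and loses power

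*Combined protocol and SAP*

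**What the plan says.** Study design and participants describes a trial run "in two academic centers", in two countries. Under Interventions, "they were randomly assigned (1:1) to active or sham tDCS", "using a permuted block approach to ensure treatment balance within each study site". Block size is not given.

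Statistical Analyses specifies the efficacy model as a repeated measures ANOVA "with randomization as the between-subjects variable, and time-point (pre- or post-intervention) as the within-subjects" factor. The model sentence is complete, and neither it nor any other sentence in the plan brings in site as a factor or covariate. The model is applied to eight outcomes, three cognitive and five self-reported. A p-value under 0.05 "was considered significant and no corrections were made for multiple comparisons".

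The same section calls the efficacy tests preliminary and gives feasibility, tolerability and safety as the pilot's main purpose.

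**The concern.** The design uses site to restrict allocation, and the analysis then ignores the restriction. Blocking removes between-site variation from the true sampling variance of the arm comparison. A model without site still counts that variation as error, so its standard error describes a noisier experiment than the one carried out.

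This matters only if the sites differ in mean pre-post change. The documents do not say whether they do. It is possible, because mindfulness training was taught in groups at each hospital ("The in-class MBSR training was conducted at the academic hospital using a group format over" about ten weeks), though the programme and workbook were common to all participants. If the sites do differ, the arm-by-time p-values are too large and the intervals too wide, and some power is lost in a small trial that has little to spare.

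**Working it through.** **Inputs from the documents.** Two sites; 1:1 allocation in permuted blocks within site; two time points; arm and time as the only model terms; alpha 0.05, taken as two-sided. The plan states no sample size, power or SD, so there is no figure of its own to reproduce.

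**Inputs assumed.** N = 28 or 40; equal sites; blocks of 4; outcome SD 1; pre-post correlation 0.6; effect 0.8 outcome SD. The SD of change is √(2 × (1 − 0.6)) = √0.8 = 0.894, so the effect is 0.8 / 0.894 = 0.89 SD of change.

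**Step 1: reduce the test to change scores.** With two time points, the arm-by-time F equals the squared two-sample t on change. In one numerical check both were 3.895. A constant site difference in level therefore cancels.

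**Step 2: what a site difference in change does.** Let d be the site difference in mean change, in within-site SDs of change (s), and p the share of participants in one site. With arms balanced within site, the variance of the arm difference depends on s² only. The residual variance without site estimates about s² × (1 + p(1 − p)d²). For equal sites:

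- site share of the variance in change: R² = (d²/4) / (1 + d²/4), so d = 2√(R²/(1 − R²));
- ratio of model SE to true SE: √(1 + [N/(N − 2)] × d²/4);
- large-sample type I error: 2 × P(Z > 1.96 / √(1 − R²)).

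For R² = 20%: d = 2√(0.2/0.8) = 1.0. The SE ratio is √(1 + (28/26) × 0.25) = 1.127 at N = 28 and √(1 + (40/38) × 0.25) = 1.124 at N = 40. Type I error is 2 × P(Z > 1.96/0.894) = 2 × P(Z > 2.19) = 2.8%.

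**Step 3: simulation.** There were 100,000 trials per setting, fitting change on arm with and without site. Monte Carlo SE is about 0.07 points for type I error and 0.15 for power.

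| Site share of variance in change | d | SE inflation | Type I, formula | Type I, N=28 / N=40 | Power without site, N=28 / N=40 |
|---|---|---|---|---|---|
| 1.5% | 0.25 | 0.7% | 4.8% | 4.9% / 4.9% | 62% / 78% |
| 5% | 0.46 | 2.7% | 4.4% | 4.5% / 4.5% | 60% / 77% |
| 10% | 0.67 | 5.7% | 3.9% | 3.9% / 4.0% | 58% / 75% |
| 20% | 1.0 | 12.5% | 2.8% | 2.9% / 2.9% | 53% / 71% |
| 30% | 1.3 | 21% | 1.9% | 2.1% / 2.0% | 46% / 65% |

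With site in the model, power is about 62% (N = 28) and 79% (N = 40); the noncentral t gives 62.4% and 78.7%. Mean bias of the effect estimate is within 0.003.

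**Step 4: sensitivity.**

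- If the effect is 0.8 SD of change, power with site is about 53% (N = 28) and 69% (N = 40). The loss at shares of 10%, 20% and 30% is 4, 9 and 15 points at both sizes.
- With unequal sites (10/18 or 14/26), power without site at 10% and 30% is 58% and 46% (N = 28), and 75% and 65% (N = 40).
- A separate simulation (10,000 trials per setting, N = 24 or 40) with 20% random dropout keeps the test conservative: 3.1% to 3.2% at d = 1.
- The same simulation with unrestricted randomisation instead of blocking gives 4.6% to 5.3%. The conservatism therefore comes from blocking by site and then leaving site out.

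**Step 5: which site term is needed.** In one simulated dataset the arm-by-time t was 2.765 without site, 2.765 with a site main effect only, and 3.027 with site by time.

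**The case against.** The strongest reply is that the harm depends on something the documents do not show. Both sites followed one programme and one workbook, and a material loss needs a gap of about one within-site SD of change. Every quantity behind the percentages is assumed. With a smaller effect, 0.5 SD of change at N = 28, power is only about 25% even with site in the model, and the loss is about 1.6 points at a 5% share and 3.3 at 10%. Among results that are non-significant without site in that setting, 2.5% and 4.4% respectively become significant with it; with the 0.89 SD effect, 6% and 11%. At modest site gaps, then, a null result mostly reflects sample size. The error is also in the safe direction, and no confirmatory claim rests on these tests.

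All of that stands as a limit on importance. It does not rescue the model: the mismatch between allocation and analysis is in the text, and correcting it is nearly free whether or not the sites differ. At large gaps the loss is real even with the smaller effect: at a 30% share, power falls from 25% to 14%.

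Two technical caveats also stand. Cancellation is exact only with complete balance, which incomplete blocks, dropout or the removal of values beyond 3 SD can disturb. And if a site ran several class groups, a two-level site term would not absorb differences between them.

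**Conclusion.** The concern holds and is minor. The efficacy model omits the factor by which allocation was blocked, and if the sites differ in mean change the arm-by-time test rejects less often than its nominal 5% and loses power. The effect estimate is unbiased and false positives do not increase.

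The documents do not determine the size. Under the assumptions above, the loss is negligible when site explains 1.5% of the variance in change and material only from about 20%. A null efficacy result could owe something to the missing site term, but at modest site gaps it would owe little.

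**What to change.** Add site (two levels) and its interaction with time to each of the eight efficacy RM-ANOVAs or, equivalently, fit change on arm and site. No arm-by-site term is needed. Confirm in the output that site by time is in the model. Regressing the post-intervention score on arm, baseline and site is an acceptable alternative but a different analysis, so choose one form and use it for every outcome.

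The document is dated June 2021, recruitment ended in March 2019 and the methods are written in the past tense, so results may already be known. In that case, keep the RM-ANOVA as described, report the site-adjusted result beside it for all eight outcomes, and label it a post hoc sensitivity analysis. With no multiplicity correction, the second set of p-values should not be used to pick out significant outcomes.

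The cost is one degree of freedom (N − 3 instead of N − 2) and, if the sites do not differ, at most 0.3 points of power. No new data are needed, because site was recorded for allocation.

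### Safety is part of the primary goal, but self-documentation is the only adverse event source described, and the definition of a serious event leaves out lasting disability and medically important events

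*Combined protocol and SAP*

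**What the plan says.** The combined protocol and SAP deals with safety in three places.

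- **Statistical Analyses** states that "the primary goal of this pilot study was to assess feasibility, tolerability, and safety" and that these measures are summarised descriptively. It gives no denominator for AEs, no list of AE summaries and no rule for missing records.
- **Outcomes** describes the participants' own records: "Participants completed hand-written logs daily, detailing their at-home use of tDCS and the frequency and duration of MBSR practice". A little further on comes the sentence about harms: "Participants also documented any failures of the tDCS device during stimulation and any adverse events (AEs"). Two groups are then singled out. One is discontinuations: "AEs that required the discontinuation of tDCS or MBSR were identified". The other is "serious adverse events (SAEs) defined as AEs that resulted in life-threatening health issues, hospitalization, or death".
- **Interventions** says that participants were trained, among other things, to "self-record necessary data". It also describes weekly hospital sessions and a coordinator who could be reached by phone for troubleshooting during home sessions.

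Outcomes adds a post-intervention assessment by blinded research staff within two weeks of the end of the intervention. None of these staff contacts is described as a point at which AEs were asked about.

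**The concern.** There are two separate gaps.

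**Ascertainment.** Stimulation was self-administered at home on six days of the week, in people aged 60 or older with cognitive complaints. If the participant's own record is the main route for AEs, the data are weakest for people who stop keeping it. Poor tolerability is one plausible reason to stop, so missingness may depend on the quantity being measured. Without a rule for missing records, a blank cannot be read: it may mean no AE or no record. If stopping differs between active and sham, the comparison between arms is affected too.

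**Classification.** The serious category rests on three outcomes. A harm can be important to the patient without being any of them. For a trial that reports safety as a main result, the count of serious events would then depend partly on a narrow definition.

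**Working it through.** The plan states no safety figure to reproduce. The check is a reading of every mention of AE collection, seriousness, staff contact, follow-up and safety analysis, followed by a formula that shows what would be needed to size the problem.

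**Step 1: routes by which an AE could be captured**

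| Contact or record | Where described | Described as an AE source? |
|---|---|---|
| Participant's own documentation | Outcomes | Yes, for any AE |
| Weekly hospital sessions | Interventions | No |
| Coordinator phone line | Interventions | No, troubleshooting only |
| Post-intervention assessment | Outcomes | No |
| Follow-up of people who stop | Not described | No |

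Self-documentation is thus the only source described. AEs leading to discontinuation and serious AEs were identified, but the text does not say by whom or how.

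**Step 2: classification under the stated rule.** All four examples below could be recorded, because participants documented any AE.

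| Event | Singled out as a discontinuation? | Classed as serious? |
|---|---|---|
| Hospital admission | Only if treatment stopped | Yes |
| Lasting disability, no admission, not life-threatening, treatment continued or already finished | No | No |
| Same event, treatment stopped because of it | Yes | No |
| Medically important event, no admission, not life-threatening, treatment continued | No | No |

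The last three rows follow from the definition alone and need no assumption about reporting behaviour.

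**Step 3: size of any under-recording.** Within an arm, let *s* be the share of randomised participants who stop recording, *p* the share of those who have an AE, and *c* the share of those with an AE for whom it is captured anyway (written down before they stopped, or found by another route). Then

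recorded AE proportion = true AE proportion − *s* × *p* × (1 − *c*).

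The shortfall is 0 if *c* = 1 and *s* × *p* if *c* = 0. Between arms,

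recorded difference = true difference − [*s*·*p*·(1 − *c*) in active − *s*·*p*·(1 − *c*) in sham].

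The documents give none of *s*, *p* or *c*, and no sample size. The formula therefore shows the mechanism and its limits but yields no number for this trial.

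**The case against.** The strongest reply is that much of this is silence rather than a stated defect.

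- **A reader might infer that AEs came only from the logs.** The text does not say so. The AE sentence names no log, and the listed log contents are device use and meditation practice. Death is among the serious outcomes and cannot be self-recorded, so some other route probably existed. This stands: the supportable wording is that self-documentation is the only source *described*.
- **A reader might infer that a lasting harm without admission would go unidentified.** That conflicts with the wording that participants documented any AE, and with the separate identification of events leading to discontinuation. This also stands: the gap in the definition concerns the serious label and does not by itself prevent recording.
- **People who stop because of a side effect are partly covered.** AEs requiring discontinuation were identified, and the event may have been written down before logging ended. Class attendance was also tracked separately, so stopping could be noticed. This narrows the concern but does not remove it. The method of identification is unstated, and later AEs, or AEs in people who stop recording for other reasons, have no described route.
- **A reader might attach a percentage to the shortfall, or ask for weekly sensation checklists by blinded staff.** Neither is supported. Any percentage would only restate assumed inputs. Interventions mentions only the MBSR instructors at the classes, and they are themselves blinded. Repeated questions about sensations could weaken the blinding of those who ask.

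The document is also dated June 2021, is written in the past tense and reports recruitment ending in March 2019, so new collection may no longer be possible.

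**Conclusion.** The concern holds in two limited parts.

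1. Safety is part of the primary goal, but no staff enquiry about AEs and no AE follow-up after stopping is described. AEs may therefore be under-recorded in people who stop recording. This assumes that no undescribed route captured those events in full; if one did, the shortfall is zero. The size cannot be computed.
2. Under the stated rule, an event causing lasting disability, or another medically important event without admission, is not serious unless it was life-threatening. This rests only on the definition as written. How many events it affects is unknown.

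The documents do not show that any event was lost. The point is a low-cost improvement to how safety is ascertained and reported.

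**What to change.** 1. **Definition.** Extend the serious-event definition to events causing lasting disability or incapacity and to events judged medically important. Apply it to every AE already documented, with the assessor blind to arm.
2. **Enquiry.** Ask every randomised participant one standard open AE question at the existing post-intervention contact. Ask it after the outcome measures, or have it asked by a coordinator who does not rate outcomes, so that rater blinding is protected. Add a coordinator call to those who stopped. Keep participants' records as a supplement.
3. **Reporting.** Report AEs, serious AEs and completeness of the AE records by arm, over all randomised participants.

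If collection is already finished, do items 1 and 3, and state possible under-recording as a limitation.

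**Cost.** One sentence in the definition, a blinded re-read of the documented AEs, one question at a visit that already exists, and a small amount of coordinator time. AE and serious AE counts may rise somewhat, and not necessarily equally in the two arms.
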